Exploratory Obj 1	Muscle spasms ³	Medical claim with an ICD-10 code in the IP, non-IP, or pharmacy setting for muscle spasms (dichotomous)	Index date to end of follow-up, where follow-up will be based on last dose of elranatamab (eg, 14 days after last recorded dose or 90 days after last recorded dose). See Section 9.7.6 for censoring criteria
Exploratory Obj 1	Musculoskeletal pain ³	Medical claim with an ICD-10 code in the IP, non-IP, or pharmacy setting for musculoskeletal pain (dichotomous)	Index date to end of follow-up, where follow-up will be based on last dose of elranatamab (eg, 14 days after last recorded dose or 90 days after last recorded dose). See Section 9.7.6 for censoring criteria
Exploratory Obj 1	COVID-19 ²	Medical claim with an ICD-10 code in the IP, non-IP, or pharmacy setting for COVID-19 (dichotomous)	Index date to end of follow-up, where follow-up will be based on last dose of elranatamab (eg, 14 days after last recorded dose or 90 days after last recorded dose). See Section 9.7.6 for censoring criteria
Infections			
Exploratory Obj 1	Sinusitis	Medical claim with an ICD-10 code in the IP, non-IP, or pharmacy setting for sinusitis (dichotomous)	Index date to end of follow-up, where follow-up will be based on last dose of elranatamab (eg, 14 days after last recorded dose or 90 days after last recorded dose).

			See Section 9.7.6 for censoring criteria
Exploratory Obj 1	Bronchitis	Medical claim with an ICD-10 code in the IP, non-IP, or pharmacy setting for bronchitis (dichotomous)	Index date to end of follow-up, where follow-up will be based on last dose of elranatamab (eg, 14 days after last recorded dose or 90 days after last recorded dose). See Section 9.7.6 for censoring criteria
Exploratory Obj 1 Exploratory Obj 1	Pneumonia ²	Medical claim with an ICD-10 code in the IP, non-IP, or pharmacy setting for pneumonia (dichotomous)	Index date to end of follow-up, where follow-up will be based on last dose of elranatamab (eg, 14 days after last recorded dose or 90 days after last recorded dose). See Section 9.7.6 for censoring criteria
Exploratory Obj 1	Adenoviral pneumonia ²	Medical claim with an ICD-10 code in the IP, non-IP, or pharmacy setting for adenoviral pneumonia (dichotomous)	Index date to end of follow-up, where follow-up will be based on last dose of elranatamab (eg, 14 days after last recorded dose or 90 days after last recorded dose). See Section 9.7.6 for censoring criteria

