		PJP Hepatitis C Hepatitis B Other infectious hepatitis Helicobacter pylori Candida esophagitis Urinary tract infection	
Effectiveness			
Exploratory Obj 2	OS	Time (in months) from index date until date of death (continuous)	Index date until censor See Section 9.7.7 for censoring criteria
Exploratory Obj 2	TTNT/D	Time (in months) from index date until the date of the next treatment (CAR-T, BsABs, bendamustine or belantamab) or death (continuous)	Index date until censor See Section 9.7.7 for censoring criteria

1. Variable will be measured as incident and prevalent. Incident cases have 30-day washout period applied
2. Variable will be measured as incident and prevalent. Incident cases have 60-day washout period applied
3. Variable will be measured as incident and prevalent. Incident cases have 14-day washout period applied

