9.7.6. Tolerability

The prevalence and incidence for each AE (Table 3) will be estimated. All prevalence and incidence estimate will be reported as a percent with corresponding 95% CIs.

$$\text{Prevalence} = \left(\frac{\text{Number of patients with an event}}{\text{Total number of patients in the cohort}} \right) \times 100$$

For the incidence analysis, only patients who did not have the event in prior to their index date will be excluded. The length of the washout is dependent on the outcome (see Table 3).

$$\text{Incidence} = \left(\frac{\text{Number of patients with an event who did not have an event at baseline}}{\text{Total number of patients in the cohort}} \right) \times 100$$

Patients will be assessed over two time periods: from the index date until 14 days or 90 days after their last administration of the index medication.

Additionally, the time to infection onset will be assessed using unadjusted Kaplan-Meier methods. The median time to event in days will be reported along with the IQR. The 95% CIs for the median time to event will be calculated using log-log transformation.

Patients will be censored at the earliest of death, the end of continuous closed-claim coverage, the latest data at the time of the specified analysis, or next treatment (CAR-T, BsABs, bendamustine or belantamab).

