Musculoskeletal pain	AE	Claims data	ICD-10 Diagnosis: M25.50, M25.522, M25.551, M25.552, M25.561, M25.562, M25.572, M25.579, M25.59, M25.612, M25.621, M25.629, M25.631, M25.641, M25.642, M25.652, M25.661, M25.662, M25.669, M25.671, M25.673, M25.674, M25.675, M25.676, M54.6, M54.81, M79.1, M79.12, M79.18, M79.621, M79.622, M79.631, M79.639, M79.641, M79.644, M79.646, M79.652, M79.659, M79.661, M79.662, M79.669, M79.671, M79.673, M79.675, M25.511, M25.512, M25.519, M25.521, M25.529, M25.531, M25.532, M25.539, M25.541, M25.542, M25.549, M25.559, M25.569, M25.571, M25.60, M25.611, M25.619, M25.622, M25.632, M25.639, M25.649, M25.651, M25.659, M25.672, M25.69, M54.89, M54.9, M79.10, M79.11, M79.601, M79.602, M79.603, M79.604, M79.605, M79.606, M79.609, M79.629, M79.632, M79.642, M79.643, M79.645, M79.651, M79.672, M79.674, M79.676	Clinical Classifications Software Refined for ICD-10-CM
COVID-19	AE - infection	Claims data	ICD-10 Diagnosis: U07.1	Pfaff et al. (2023)
Adenoviral pneumonia	AE - infection	Claims data	ICD-10 Diagnosis: J12.0	Cocoros et al. (2024)

Cytomegaloviral pneumonitis	AE - infection	Claims data	ICD-10 Diagnosis: B25.0	ICD-10data.com
Other pneumonia	AE - infection	Claims data	ICD-10 Diagnosis: J12.1, J12.2, J12.81, J12.3, J12.89, J12.9, J13, J18.1, J15.0, J15.1, J14, J15.4, J15.3, J15.20, J15.211, J15.212, J15.29, J15.8, J15.5, J15.6, A48.1, J15.9, J15.7, J16.0, J16.8, A37.01, A37.11, A37.81, A37.91, A22.1, B44.0, J17, B77.81, J18.0, J18.8, J18.9, J10.00, J10.01, J10.08, J11.00, J11.08	Smithee et al. (2020)
Pneumonia	AE - infection	Claims data	An ICD-10 Diagnosis Code for any of the following types of pneumonia. See the following rows for infection type: Adenoviral pneumonia, cytomegaloviral pneumonia, other pneumonia	
Upper respiratory tract infection	AE - infection	Claims data	ICD-10 Diagnosis: A38.0-A38.9, J02.0-J03.91, J01.00-J01.91, J09.x1-J11.89, J00, J04.0-J06.9, H65.00-H65.199, H68.011-H68.019, J20.0-J20.9, J45.20-J45.998, J45.21, J45.31, J45.41, J45.51, J45.901	Butler et al. (2023)
Acute sinusitis	AE - infection	Claims data	ICD-10 Diagnosis: J01.x0	Savage et al. (2023)
Bronchitis	AE - infection	Claims data	ICD-10 Diagnosis: J20.0-J20.9	Butler et al. (2023)
Sepsis	AE - infection	Claims data	ICD-10 Diagnosis: A02.1, A22.7, A26.7, A32.7, A40.0, A40.1, A40.3, A40.8, A40.9, A41.01, A41.02, A41.1, A41.2, A41.3, A41.4, A41.50, A41.51, A41.52, A41.53, A41.59, A41.81, A41.89, A41.9, A42.7, A54.86, B37.7, R65.20, R65.2	Prasad et al. (2021)

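### Table 3 sets no washout for sinusitis and bronchitis, so their incidence is not defined, and the sinusitis code list is narrower than its label

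*Protocol*

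**What the plan says.** Section 9.7.6 sets the scope: "The prevalence and incidence for each AE (Table 3) will be estimated". It says that the washout depends on the outcome and refers to Table 3 for its length. Its incidence formula counts patients with an event who had none at baseline.

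The lengths stand only in the three footnotes to Table 3 in Section 9.3:
- footnote 1: "Incident cases have 30-day washout period applied"
- footnote 2: "Incident cases have 60-day washout period applied"
- footnote 3: "Incident cases have 14-day washout period applied"

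Each footnote also states that the marked variable is measured both as incident and as prevalent.

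The two rows at issue are defined as "Medical claim with an ICD-10 code in the IP, non-IP, or pharmacy setting for sinusitis (dichotomous" and "Medical claim with an ICD-10 code in the IP, non-IP, or pharmacy setting for bronchitis (dichotomous". Neither variable name carries a footnote mark.

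In Annex 2 the sinusitis row is labelled as acute sinusitis and its code list is "ICD-10 Diagnosis: J01.x0". The upper respiratory tract infection row contains "J02.0-J03.91, J01.00-J01.91, J09.x1-J11.89" and, further on, J20.0-J20.9. J20.0-J20.9 is also the entire bronchitis list.

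**The concern.** Section 9.8 says the protocol will be strictly followed, but for these two rows Section 9.7.6 points to a rule that Table 3 does not contain. The analysis covers two cohorts and, after the initial results, four data refreshes. An analyst has to supply the look-back, and different choices give different incidence figures under the same label. A reader who compares sinusitis or bronchitis with the other infections would assume a common 60-day rule that the protocol does not give.

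The sinusitis codes raise a second question. The table promises sinusitis without restriction, and the annex delivers part of the J01 range that the same annex uses elsewhere. Infection is the most frequent adverse event in the trial that the protocol cites as background (69.9%), so the infection rows are likely to be read closely.

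**Working it through.** No sample size, power or event count is involved, so the check is a row count and a comparison of code lists.

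**Step 1: washout marks in Table 3.** I counted all adverse event rows, leaving out time to infection onset.

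| Mark | Washout | Rows |
|---|---|---|
| Footnote 1 | 30 days | 10 |
| Footnote 2 | 60 days | 16 |
| Footnote 3 | 14 days | 10 |
| None | not stated | 2 (Sinusitis, Bronchitis) |

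10 + 16 + 10 = 36 of 38 rows have a washout. Footnote 2 covers renal failure and 15 infections (COVID-19 included). Among the infections, 15 of 17 have 60 days and the remaining two have nothing.

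**Step 2: what an analyst could do.** The incidence formula still asks for no event at baseline, so the missing element is the length of the look-back. Three readings are open:
- no washout, because no footnote applies one;
- 60 days, by analogy with the other infections;
- MM diagnosis to one day before index, the window that Table 2 gives for any infection, where sinusitis and bronchitis are both named.

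**Step 3: the readings give different answers.** Take two patients who each have a J20.0-J20.9 claim after index. Patient A also has one within the 60 days before index. Patient B has one earlier than that, but after MM diagnosis.

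| Rule applied | Patient A incident? | Patient B incident? |
|---|---|---|
| Upper respiratory tract infection, 60 days as printed | no | yes |
| Bronchitis, no washout | yes | yes |
| Bronchitis, 60 days | no | yes |
| Bronchitis, since MM diagnosis | no | no |

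Relative to the 60-day rule, one reading adds cases and another removes them.

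**Step 4: sinusitis codes.** J01.x0 contains only codes ending in 0. The upper respiratory range runs to J01.91, so at least one code ending in 1 is treated as an infection there and lies outside the sinusitis list. For a patient whose only infection claim after index is J01.91:
- upper respiratory tract infection row: counted;
- sinusitis row: not counted;
- time to infection onset: no event, because its list names sinusitis but not upper respiratory tract infection.

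Bronchitis has no such gap, since its list and the J20 part of the upper respiratory list are identical.

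**The case against.** The strongest reply is that a missing footnote is not a washout of zero. A reader might infer that, for these two rows, incidence equals prevalence and is inflated by infections present before the first dose. The protocol does not support that. The numerator in Section 9.7.6 removes patients with an event at baseline for every adverse event, these two included. With the longest look-back, incidence would be lower than under 60 days. Any figure in percentage points would need assumed rates of prior and repeat claims, which the protocol does not give. This part of the objection stands, and the finding is limited to an unset look-back. One sentence in Section 9.7.6 also words the baseline exclusion the wrong way round, but that affects all adverse events alike.

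The unmarked rows might be meant as prevalence only, since the footnotes also carry the incident-and-prevalent statement. That would conflict with the requirement of incidence for each adverse event, so the text needs reconciling either way.

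A reader might also infer that recurrent sinusitis is missed altogether. The protocol does not say what a final 1 means, and those codes remain captured under upper respiratory tract infection. The annex openly labels its row as acute. What remains is that the Table 3 label and the annex list differ, and that the codes drop out of two outcomes.

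Two smaller points. The rows are the only unmarked ones within Table 3, but Annex 2 also lists rash as an adverse event with no Table 3 row, and hence no washout. Marks lost in reading the PDF cannot be excluded, but the other 36 survived. Sinusitis and bronchitis are also missing from the any-infection list in Annex 2 although Table 2 names them, which suggests that they were not carried through the document.

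**Conclusion.** The point holds as a gap in definition. For sinusitis and bronchitis the protocol requires an incidence and does not fix its baseline look-back, so these two figures are not comparable with the other 15 infections. The clearest internal evidence is that identical J20.0-J20.9 claims have a 60-day rule under one row and no stated rule under another.

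The code mismatch is a separate, printed rule that changes results: J01 codes ending in 1 never count as sinusitis or in time to infection onset.

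The size of either effect cannot be derived from the protocol. For incidence the direction is also unknown, because the look-back could be shorter or longer than 60 days and the narrow sinusitis list would define the baseline event as well as the outcome. The conclusion assumes that the absent marks are absent in the source document. Both variables belong to an exploratory objective, are reported descriptively and are not formally compared between cohorts. This is therefore a minor correction.

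**What to change.** 1. In Table 3, add footnote 2 (60-day washout, incident and prevalent) to the Sinusitis and Bronchitis rows. If prevalence only was intended, say so there and exempt the two rows in Section 9.7.6.
2. In Annex 2, change the sinusitis list from J01.x0 to J01.00-J01.91, the range already used in the annex. Alternatively, keep J01.x0 and relabel sinusitis in Table 3, including in the time to infection onset list, to match it.
3. In the final report, state which look-back and code list earlier deliveries used for these two rows.

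The cost is two footnote marks, one code-list entry or label, and a rerun of the affected rows at a planned refresh. No new data are needed.

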Exploratory Obj 1	Cytomegaloviral pneumonitis ²	Medical claim with an ICD-10 code in the IP, non-IP, or pharmacy setting for cytomegaloviral pneumonitis (dichotomous)	Index date to end of follow-up, where follow-up will be based on last dose of elranatamab (eg, 14 days after last recorded dose or 90 days after last recorded dose).

			
See Section 9.7.6 for censoring criteria

Exploratory Obj 1	Other pneumonia ²	Medical claim with an ICD-10 code in the IP, non-IP, or pharmacy setting for pneumonia other than adenoviral or cytomegaloviral pneumonia (dichotomous)	
Index date to end of follow-up, where follow-up will be based on last dose of elranatamab (eg, 14 days after last recorded dose or 90 days after last recorded dose).
 
See Section 9.7.6 for censoring criteria

Exploratory Obj 1	Upper respiratory tract infection ²	Medical claim with an ICD-10 code in the IP, non-IP, or pharmacy setting for upper respiratory tract infection (dichotomous)	
Index date to end of follow-up, where follow-up will be based on last dose of elranatamab (eg, 14 days after last recorded dose or 90 days after last recorded dose).
 
See Section 9.7.6 for censoring criteria

Exploratory Obj 1	Sepsis ²	Medical claim with an ICD-10 code in the IP, non-IP, or pharmacy setting for sepsis (dichotomous)	
Index date to end of follow-up, where follow-up will be based on last dose of elranatamab (eg, 14 days after last recorded dose or 90 days after last recorded dose).
 
See Section 9.7.6 for censoring criteria

Exploratory Obj 1 Exploratory Obj 1	Cytomegaloviral infection ²	Medical claim with an ICD-10 code for PJP (dichotomous)	
Index date to end of follow-up, where follow-up will be based on last dose of elranatamab (eg, 14 days after last recorded dose or 90 days after last recorded dose).
 
See Section 9.7.6 for censoring criteria

Exploratory Obj 1	PJP ²	Medical claim with an ICD-10 code for PJP (dichotomous)	Index date to end of follow-up, where follow-up will be based on last dose of elranatamab (eg, 14 days after last recorded dose or 90 days after last recorded dose). See Section 9.7.6 for censoring criteria

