Exploratory Obj 1	Hepatitis C ²	Medical claim with an ICD-10 code in the IP, non-IP or pharmacy setting for hepatitis C (dichotomous)	Index date to end of follow-up, where follow-up will be based on last dose of elranatamab (eg, 14 days after last recorded dose or 90 days after last recorded dose). See Section 9.7.6 for censoring criteria
Exploratory Obj 1	Hepatitis B ²	Medical claim with an ICD-10 code in the IP, non-IP or pharmacy setting for hepatitis B (dichotomous)	Index date to end of follow-up, where follow-up will be based on last dose of elranatamab (eg., 14 days after last recorded dose or 90 days after last recorded dose). See Section 9.7.6 for censoring criteria
Exploratory Obj 1	Other infectious hepatitis ²	Medical claim with an ICD-10 code in the IP, non-IP or pharmacy setting for other infectious hepatitis (dichotomous)	Index date to end of follow-up, where follow-up will be based on last dose of elranatamab (eg., 14 days after last recorded dose or 90 days after last recorded dose). See Section 9.7.6 for censoring criteria
Exploratory Obj 1	Helicobacter pylori ²	Medical claim with an ICD-10 code in the IP, non-IP or pharmacy setting for helicobacter pylori (dichotomous)	Index date to end of follow-up, where follow-up will be based on last dose of elranatamab (eg, 14 days after last

			recorded dose or 90 days after last recorded dose). See Section 9.7.6 for censoring criteria
Exploratory Obj 1	Candida esophagitis ²	Medical claim with an ICD-10 code in the IP, non-IP or pharmacy setting for candida esophagitis (dichotomous)	Index date to end of follow-up, where follow-up will be based on last dose of elranatamab (eg, 14 days after last recorded dose or 90 days after last recorded dose). See Section 9.7.6 for censoring criteria
Exploratory Obj 1	Urinary tract infection ²	Medical claim with an ICD-10 code in the IP, non-IP or pharmacy setting for a urinary tract infection (dichotomous)	Index date to end of follow-up, where follow-up will be based on last dose of elranatamab (eg, 14 days after last recorded dose or 90 days after last recorded dose). See Section 9.7.6 for censoring criteria
Exploratory Obj 1	Time to infection onset	Time in days from index date to first infection for the following infections: COVID-19 Sinusitis Bronchitis Adenoviral pneumonia Cytomegaloviral pneumonitis Pneumonia Sepsis Cytomegaloviral infection	Index date until censor See Section 9.7.6 for censoring criteria

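### Time to infection onset does not exclude infections already present at index, omits upper respiratory tract infection from its list, and leaves its post-dose window unclear

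*Protocol*

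**What the plan says.** Table 3 (Section 9.3) defines time to infection onset as "Time in days from index date to first infection for the following infections" and then names 15 infections. Its assessment period is "Index date until censor", with a pointer to Section 9.7.6. The row has no footnote marker.

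Most of the individual infection rows in the same table carry footnote 2: "Variable will be measured as incident and prevalent. Incident cases have 60-day washout period applied". Sinusitis and bronchitis carry no footnote. All of the individual infection rows, including those two, tie follow-up to the last dose, with 14 and 90 days as the limits.

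Section 9.7.6 mentions prior events once: "For the incidence analysis, only patients who did not have the event in prior to their index date will be excluded". Read literally, that sentence removes the wrong patients, but the incidence formula below it makes the intent clear. In either case its scope is the incidence analysis. The section then says that patients are followed "from the index date until 14 days or 90 days after their last administration of the index medication", introduces the Kaplan-Meier analysis of infection onset, and closes with a censoring list of death, loss of closed-claim coverage, end of data and next treatment.

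**The concern.** An onset analysis is meant to show when new infections appear after the drug is started. Here the clock starts on the index date and any listed code from that day counts. A patient treated for a urinary tract infection on Day -3 who has a follow-up claim on Day 2 becomes an onset at two days. A hepatitis B or C carrier whose chronic code is recorded at the first post-index visit becomes an onset within days of the first dose.

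This is the only timing estimate for infections that the protocol plans. Infections are also the most frequent adverse event it cites from the phase 2 trial (69.9%, Section 7). A median shortened by old infections would be read as early toxicity. The incidence reported beside it would rest on a different at-risk population, a different list of infections and possibly a different follow-up window.

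**Working it through.** The protocol states no infection rate, baseline infection prevalence or expected median, so there is no planned figure to reproduce. The check compares texts and adds an illustration on assumed inputs.

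**1. Washout.** Incidence: 60 days by footnote 2 for most infection types; none stated for sinusitis or bronchitis. Time to onset: none in the row and none in Section 9.7.6. Under the text as written, a pre-index infection that is coded again on or after the index date is an event.

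**2. Chronic hepatitis.** Annex 2 defines hepatitis B to include B18.0 and B18.1, and hepatitis C to include B18.2. The same annex uses B18.x as a baseline Charlson component (mild liver disease). One code family thus serves as a baseline comorbidity and as an onset event.

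**3. The list.** Table 3 has 17 infection rows; the onset list has 15 entries. The two not named are other pneumonia and URTI. Annex 2 builds pneumonia from adenoviral, cytomegaloviral and other pneumonia, so other pneumonia is covered. URTI is the only type omitted, although it is in the baseline any-infection definition of Table 2 and Annex 2.

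**4. Which URTI codes are lost.** J20.x enters through bronchitis, J01.x0 through sinusitis, and J10.00, J10.01, J10.08, J11.00 and J11.08 through other pneumonia. J00, J02 to J06 and most of J09 to J11 enter nowhere. The URTI list also contains "H65.00-H65.199, H68.011-H68.019, J20.0-J20.9, J45.20-J45.998", and Annex 2 classes J45.x under chronic pulmonary disease. Adding URTI unchanged would count asthma as an infection.

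**5. Window.** The individual infection rows state 14/90 days. The onset row does not. The Section 9.7.6 censoring list does not either, but it omits the limit for all adverse events.

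**6. Direction and illustration.** Assume that a share q of patients has a carried-over claim at about day 0, and that the rest have exponential onset with true median m. Then S(t) = (1 − q) × 2^(−t/m). Setting this to 0.5 gives an apparent median of m × ln(2(1 − q))/ln 2.

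| Assumed q | Apparent / true median |
|---|---|
| 5% | 0.926 |
| 10% | 0.848 |
| 20% | 0.678 |
| 30% | 0.485 |

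With an assumed hazard of 0.10 per month, m = ln 2/0.10 = 6.93 months. The apparent median is then ln(1.8)/0.10 = 5.88 months at q = 10% and ln(1.4)/0.10 = 3.36 months at q = 30%.

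Omitting URTI works the other way, but only if onset is a composite. If the lost codes carried a share u of the hazard, the median would lengthen by 1/(1 − u): 1.25-fold at an assumed u of 20% and 1.43-fold at 30%. Here u must exclude the codes that still enter under step 4.

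**The case against.** **The 14/90-day limit.** A reader might infer that the onset analysis ignores it, so that infections long after the last dose are counted. The documents do not support that. The sentence in Section 9.7.6 stands under tolerability in general, the onset paragraph follows it directly, and the onset row refers to that section. The censoring list proves nothing, because it omits the limit even for outcomes to which it plainly applies. What remains is an ambiguity: the onset row is worded differently from every other infection row.

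**URTI never counted.** This too would be an overstatement. URTI has its own row and is counted in prevalence and incidence, and part of its code set reaches the onset analysis under other names. The loss is confined to this analysis and to the unshared codes. The authors may have meant sinusitis and bronchitis to stand in for URTI, but the protocol does not say so.

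**Comparison with prevalence.** Prevalence applies no washout either, so an onset analysis without washout does not conflict with it on that count. The washout mismatch is with incidence.

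**Composite or per type.** The definition can be read either way. Listing pneumonia beside two of its subtypes makes more sense per type. On that reading, hepatitis carriers affect only the hepatitis results and omitting URTI moves no other median. This stands, and the wording should settle it.

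**An analysis plan may add a washout.** It may. But Table 3 is where the protocol assigns washouts and lists the infections, and Section 9.8 commits the analysts to follow the protocol strictly. As written, the rule is no exclusion.

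**Conclusion.** The point holds on two counts and, on a third, as an ambiguity. No exclusion of infections present at index is stated for time to onset, so carried-over claims and chronic hepatitis codes count as early onsets. URTI is missing from the closed list without a stated reason. Whether follow-up ends 14 or 90 days after the last dose is unclear.

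The carry-over bias runs towards a median that is too early. Its size cannot be derived from the documents. The ratios shown rest on assumed carry-over shares, exponential onset and a median that is reached. Read per type, q applies to each infection separately. On a composite reading the URTI omission pushes the other way, and nothing suggests that the two offset each other.

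The outcome is exploratory and descriptive, with no formal comparison, so no sample size, power or error rate is affected. It should be corrected because it is cheap to correct and the median would otherwise be misread.

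**What to change.** In Table 3 and Section 9.7.6:

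- For each infection type, restrict the onset analysis to patients without that infection in the 60 days before index, as in footnote 2. The 180-day enrolment requirement already covers this lookback.
- Give sinusitis and bronchitis the same 60-day washout. Otherwise a sinusitis episode on Day -3 remains unhandled.
- Report chronic hepatitis codes separately, or count them only where the available history holds no earlier code. A 60-day lookback can miss a carrier who was last coded before then.
- Add URTI to the list, with J45.x removed from its codes.
- State whether onset is per type, a composite, or both. For a composite, say whether a patient with one recent infection leaves the analysis or stays at risk for the other types.
- State that follow-up ends 14 or 90 days after the last administration, with both versions reported, as for the other adverse events.

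The cost is protocol wording, reprogramming of one endpoint, and slightly smaller denominators for the infection types that some patients had just before index.
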